11.2. Concomitant Therapies

Concomitant therapies are any new or existing therapy received from Visit 1 until discharge from the study.

Concomitant therapies include drug (*e.g.*, prescription, over-the-counter [OTC]) and non-drug (*e.g.*, chiropractic, physical therapy, energy-based treatments) therapies. Subjects will refrain from receipt of any therapy in compliance with the inclusion/exclusion criteria. Subjects should refrain from changing the use of any concomitant therapies during the study.

All new or modified concomitant therapies used during the study must be recorded in the subject CRF.

11.3. Prohibited Therapies

During the course of this study, subjects are prohibited from using the following treatment therapies to treat the identified common warts:

- Intralesional Therapy
 - Immunotherapy (e.g., *Candida* antigen, mumps antigen, *Trichophyton* antigen)
 - Anti-metabolite therapy (e.g., bleomycin, 5-fluorouracil);
- Systemic Therapy
 - Immunomodulatory/immunosuppressant therapy (e.g., etanercept, alefacept, infliximab);
 - Glucocortico-steroids (inhaled and intra-nasal steroids are permitted);
- Topical Therapy
 - LASER (e.g., pulsed-dye laser [PDL], light (e.g., intense pulsed light [IPL], photodynamic therapy [PDT], other energy-based therapy);
 - Immuno-therapy (e.g., imiquimod, squaric acid dibutyl ester [SADBE], etc.);
 - Anti-metabolite therapy (e.g., 5-fluorouracil);
 - Retinoids;
 - Liquid nitrogen, electrodesiccation, curettage;
 - Over-the-counter (OTC) wart therapies and cantharidin.

The investigator should notify the Medical Monitor immediately if any prohibited therapies are required to ensure subject safety.

For subjects starting an 8-week treatment schedule for an identified wart, topical products (e.g., moisturizers, sunscreens, etc.) must not be applied to any of their identified common warts **within 12 hours prior** to any treatment application (Note: routine cleansing products are allowed).

After the completion of a treatment application, subjects must **NOT wash/submerge** the treated common wart for at least **6 hours** and must not apply any topical products to the treated common wart for at least **6 hours**. Parents/legal guardians of children must ensure that the child does not put the treated area in their mouth, or eyes, until completely dry after the application. If the treated area is not completely dry 10 minutes after the application, the area should be blotted dry.

12. ASSESSMENT OF SAFETY

In addition to reporting adverse events throughout the study the investigator, a designated and appropriately trained staff member or the subject, will perform the following safety assessments according to the schedules noted below.

12.1. Local Skin Reactions (LSRs)

The LSR assessment is the Investigator's assessment of the signs and the subject's assessment of the symptoms associated with irritation at the identified common wart site (*i.e.*, the common wart and the skin immediately surrounding the common wart exposed to study medication).

The Local Skin Reaction signs to be assessed are:

- Erythema
- Edema
- Erosion
- Ulceration
- Vesicles/bullae
- Excoriations
- Scabbing

The Local Skin Reaction symptoms to be assessed (by the Subject) are:

- Stinging/burning
- Pruritus (itch)

The Investigator will evaluate the LSR signs at the each identified common wart site as follows:

- At visits where a study medication treatment or retreatment is performed:
 - Perform an LSR assessment prior to any study medication application
 - and

The Subject will assess the LSR symptoms at the identified common wart site as follows:

- At visits where a study medication treatment or retreatment is performed:
 - Perform an LSR assessment prior to any study medication application

At visits where **NO** study medication treatment is performed:

- Perform an LSR assessment.

Subjects are to remain in the clinic for 20 minutes after the application of their study medication. Any local skin reactions or other adverse experiences that occur during this time period must be

Aclaris Therapeutics, Inc.

Protocol Number: A-101-WART-303

Protocol Version 3: 14 February 2019

documented as an adverse event.

The Investigator and Subject should report the one integer that best describes the severity of each LSR sign or LSR symptom for the common wart site using the scale below:

Local Skin Reactions	
Grade	Descriptor
0	None OR No signs or symptoms present.
1	Asymptomatic or mild symptoms OR clinical or diagnostic observations only OR intervention not indicated.
2	Moderate OR minimal, local or noninvasive intervention indicated.
3	Severe or medically significant but not immediately life threatening OR disabling OR limiting self-care of activities of daily living.

12.2. Clinical Laboratory Sampling

Subjects that do not have their Visit 1 the same day as Visit 13 of either A-101-WART 301 or A-101-WART 302 will have to have a clinical chemistry and CBC performed. Non-fasting blood samples for clinical laboratory analysis will be collected by a qualified staff member on Day 182 for all subjects. Approximately 7.5 mL of blood will be collected for each chemistry sample and 3 ml of blood will be collected for each complete blood count (CBC). These blood samples will be sent to a central laboratory for analysis. Refer to the study specific laboratory manual for instructions regarding handling of the blood samples and shipping instructions.

The following tests, at a minimum, will be conducted:

Chemistry Panel	Complete Blood Count
Albumin	Hematocrit
Alkaline phosphatase	Hemoglobin
Alanine aminotransferase (ALT)	Platelet count
Aspartate aminotransferase (AST)	Red blood cell morphology
Blood urea nitrogen (BUN)	Red blood cell count
Bicarbonate	White blood cell count
Calcium	White blood cell differential
Chloride	% & absolute
Creatinine	Basophils
Glucose	Eosinophils

Aclaris Therapeutics, Inc.

Protocol Number: A-101-WART-303

Protocol Version 3: 14 February 2019

Lactate dehydrogenase (LDH)	Lymphocytes
Phosphorus	Monocytes
Potassium	Neutrophils
Sodium	
Total bilirubin	
Total protein	
Uric acid	

The results of the clinical laboratory tests will be reported on the central laboratory's standard reports. These laboratory results will be sent to the investigator via fax. The investigator must review all laboratory reports in a timely manner and note NCS or CS to define the clinical relevance of any result that is outside the normal range for the laboratory. The investigator must date and initial every laboratory report.

The investigator must report all laboratory results that are BOTH outside the normal range for the laboratory AND, in the opinion of the investigator, CS as medical history if found prior to the first study medication treatment or as an AE if found after the first study medication treatment begins.

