13. ADVERSE EVENTS

13.1. Definitions

13.1.1. Adverse Events (AEs)

An adverse event (AE) is any untoward medical occurrence in a patient that develops or worsens in severity during the conduct of a clinical study of a pharmaceutical product and does not necessarily have a causal relationship to the study drug. An adverse event can, therefore, be any unfavorable and unintended physical sign, symptom, or laboratory parameter that develops or worsens in severity during the course of the study, or significant worsening of the disease under study (or any concurrent disease), whether or not considered related to the study drug.

Accordingly, an adverse event could include any of the following:

- intercurrent illnesses;
- physical injuries;
- events possibly related to concomitant medication;
- significant worsening (change in nature, severity, or frequency) of the disease under study or other pre-existing conditions. (NOTE: A condition, recorded as pre-existing, that is intermittently symptomatic [e.g., headache] and which occurs during the study should be recorded as an adverse event);
- Drug interactions;
- Events occurring during diagnostic procedures or any washout phase of the study;
- laboratory or diagnostic test abnormalities occurring after the start of the study (i.e., after screening and once confirmed by repeat testing) that results in the withdrawal of the patient from the study, requires medical treatment or further diagnostic work-up, or is considered by the study investigator to be clinically significant. NOTE: Abnormal laboratory test results at the screening visit that preclude a patient from entering the study or receiving study treatment are not considered adverse events, but will be recorded to monitor data from patients who do not meet screening criteria.

The investigator must, for any common wart related AE, question the subject in detail to determine if there are any confounding factors (e.g., irritation by clothing or activity, sunburn) for any such AE.

The investigator should, when certain, report a diagnosis rather than the signs, symptoms or clinically relevant abnormal laboratory values associated with the AE. Otherwise, signs, symptoms or abnormal laboratory values may be used to describe the AE.

Any CS abnormality discovered prior to the first study medication treatment should be reported as medical history, not as an AE.

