## **3.11 Safety Analyses**

Safety summaries will be conducted on the Safety Population.

The following sections detail the summaries performed on the safety data. Additional data handling rules including those for imputation of partially missing dates are provided in a separate SAP document pertaining to data handling and programming specifications.

The baseline scores for laboratory assessments and local skin reactions will be the last non-missing value collected before first application of A-101 45% in this study. For most subjects, Visit 1 laboratory measurements in this study are done on Visit 13 of parent double-blind study (A-101-WART-301 or A-101-WART-302).

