### **3.11.2 Adverse Events**

Adverse events are coded using the MedDRA (Version 22) and are categorized by system organ class (SOC) and preferred term (PT). Only treatment emergent adverse events are included in summary tabulations (i.e. adverse events occurring within 30 days of each application of study medication). All adverse events are included in the data listings including those that are not considered treatment emergent.

To allow differentiation as to which study period an Adverse Event occurred, three categories are defined based upon onset date. Adverse Events that had onset dates prior to the first application of study medication are considered "prior". Adverse events with onset dates on or within 30 days of an application of study medication are considered "treatment emergent". Events with onset dates more than 30 days after the most recent application of study medication are considered as "post-therapy." In this study, subjects can possibly receive medication up to three cycles and multiple doses of medication within a treatment cycle. The above rule will be applied to all known doses of medication while determining study period.

Frequency tabulations are presented by MedDRA SOC and preferred term, for all adverse events; study treatment-related adverse events, adverse events resulting in discontinuation of study treatment, serious adverse events and adverse events by maximum severity. Adverse events resulting in discontinuation are those with 'action taken' recorded as 'drug withdrawn'.

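### Protocol 12.2 classes clinically significant laboratory results by when they are found, so a pre-dose baseline value read after dosing can be counted as treatment emergent

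*Protocol*

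**What the plan says.** Protocol 12.2 applies to results that are both outside the normal range and, in the investigator's opinion, clinically significant. These are to be reported as medical history if they come to light before the first treatment, and "as an AE if found after the first study medication treatment begins". The last sentence of 13.1.1 follows the same logic: "Any CS abnormality discovered prior to the first study medication treatment should be reported as medical history, not as an AE". Neither sentence mentions when the blood was drawn.

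Other text uses a different test:

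- Protocol 13.1.1 defines an AE as "any untoward medical occurrence in a patient that develops or worsens in severity during the conduct of a clinical study". Its laboratory bullet is limited to abnormalities that occur after screening and are confirmed by a repeat test.
- Protocol 13.1.3 makes non-serious events that occur between consent and first application medical history.
- SAP 3.11 says the laboratory baseline "will be the last non-missing value collected before first application of A-101 45% in this study".

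On the source of the baseline sample, SAP 3.11 states: "For most subjects, Visit 1 laboratory measurements in this study are done on Visit 13 of parent double-blind study". Under Protocol 12.2, subjects whose Visit 1 is not on the parent Visit 13 day "will have to have a clinical chemistry and CBC performed". Samples go to a central laboratory and results come back by fax. Protocol 10.5 has subjects with warts at entry make their first application in the office on Day 1.

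On tabulation, SAP 3.11.2 says: "Adverse events with onset dates on or within 30 days of an application of study medication are considered" treatment emergent. Only events with onset before the first application are prior, and only treatment-emergent events enter the summary tables.

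**The concern.** The protocol has two tests for the same result, discovery and occurrence, and the SAP adds a third for the baseline, collection. They agree when a report is read before dosing. They part when the sample is drawn and the first dose is given on the same day, which the design expects for subjects with warts at entry.

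In that case a value that was abnormal before any open-label dose can be tabulated as an event arising on A-101, in a study whose primary objective is safety. The same number would serve as the subject's pre-treatment baseline in the laboratory tables. The misclassification can run only towards counting a pre-existing abnormality as treatment emergent. It could also vary by site, according to whether staff follow 12.2 or 13.1.3.

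**Working it through.** The plan gives no figure to reproduce. The check traces one case through the rules, followed by some day counting.

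**Case.** A subject has warts at entry. The baseline blood is drawn on Day 1 before the first application, either as the 303 Visit 1 sample or as the parent Visit 13 sample on the same day. The result is out of range and judged clinically significant. The faxed report is read after the Day 1 application, since nothing in the protocol requires it to be reviewed first.

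| Rule | Test | Result |
|---|---|---|
| Protocol 12.2 | found after first treatment | AE |
| Protocol 13.1.1, last sentence | discovered before first treatment | does not apply, so no protection |
| Protocol 13.1.3 | occurred between consent and first application | medical history |
| Protocol 13.1.1, laboratory bullet | occurred after screening, confirmed by repeat | not an AE if already present at screening |
| SAP 3.11 | collected before first application | baseline value |

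**If the site follows 12.2**, SAP 3.11.2 gives:

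- Onset dated to the sample (Day 1): this is the day of an application, so treatment emergent. The rule uses dates only and cannot separate before from after within the day.
- Onset dated to the report: treatment emergent if within 30 days of an application. In a full course from Day 1 the last application is Day 53 (Protocol 10.5), and 53 + 30 = 83, so any report date up to Day 83 qualifies.

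Both dating conventions give the same class. A repeat test drawn after dosing that confirms the abnormality would also fall inside the window.

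**Which scheduled samples can produce a laboratory treatment-emergent event?** The only scheduled post-baseline sample is Day 182. A full course starting on day s has its last application on day s + 52 (53 − 1 = 52).

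- s = 1: last application Day 53; 182 − 53 = 129 days, outside 30.
- s = 60: last application Day 112; 182 − 112 = 70 days, outside 30.
- Limit: 182 − (s + 52) ≤ 30 gives s ≥ 100.
- s = 122, the latest start allowed by Protocol section 6: last application Day 174; 182 − 174 = 8 days, inside 30.

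For a single course from Day 1, no scheduled post-dose sample therefore falls in the window, and a clinically significant Day 182 result would be classed as post-therapy. Courses started at about Day 100 to 122 do bring Day 182 inside it. Visit and application windows move these limits by only a few days.

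**Number affected.** The documents give no rate of clinically significant baseline values and no count of subjects dosed on Day 1. Purely as an illustration, assume 200 to 350 such subjects and a rate of 0.5% to 2%: 200 × 0.005 = 1 and 350 × 0.02 = 7. Both inputs are assumptions; the result shows only that the count is likely to be small.

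**The case against.** The strongest reply is that section 13 already supplies the right rule. Protocol 13.1.3 and the laboratory bullet in 13.1.1 turn on occurrence, so an investigator has textual grounds for recording a pre-dose abnormality as medical history. That is fair, and it means misreporting is not certain. It does not remove the problem: 12.2 is the mandatory, laboratory-specific instruction and gives the opposite answer. The passages contradict each other and must be reconciled.

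Other parts of the reply stand as limits:

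- For most subjects the baseline is a parent Visit 13 sample. How a finding there is reported also depends on the 301/302 rules, which are not in the documents.
- That the draw precedes the application is inferred from the SAP's baseline definition; the protocol does not state it.
- A diagnosis reported in place of a laboratory value, with onset before Day 1, would be classed as prior.
- SAP 3.11 refers to a separate data-handling document, not available here, which may contain an onset rule.
- Subjects clear at Visit 1 and treated later have no scheduled draw at treatment start, so the same-day problem does not normally reach them.

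A reader might infer that nearly everyone treated on Day 1 is affected. The documents do not support that: many subjects may come under the rule, but it bites only on results that are both out of range and clinically significant. A reader might also infer that laboratory treatment-emergent rows for single-course subjects can hold nothing but pre-dose findings. That too goes too far, because repeat tests and unscheduled or early-termination visits can yield samples inside the window.

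**Conclusion.** The point holds as a contradiction between rules with a predictable direction of error. Where the baseline sample and the first application share a day and the report is read afterwards, a literal reading of 12.2 together with SAP 3.11.2 turns a clinically significant baseline value into a treatment-emergent AE. The words treatment emergent come from the SAP; 12.2 says only AE.

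The number of subjects cannot be computed and is probably small. The shift and change-from-baseline tables are unaffected, because their baseline already goes by collection. The effect is confined to laboratory entries in the AE tables. It has some weight there because, for a single course from Day 1, the baseline is the only scheduled sample that can fall within the 30-day window. It would be wrong to conclude that the laboratory safety analysis as a whole is biased.

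This rests on the baseline draw preceding the application, on same-day draw and dosing, and on no overriding onset rule in the separate data-handling document. The correction is worth making because the rule is plainly inconsistent and cheap to repair.

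**What to change.** **Protocol 12.2 and the last sentence of 13.1.1.** Reconcile both with 13.1.3 by classifying on sample collection time relative to the first open-label application. A clinically significant value collected before it is medical history for this study, whenever the report is read. A value collected later is an AE if new or worse than baseline. State that parent Visit 13 findings remain reportable under the parent study's rules, so that an abnormality following double-blind treatment is not lost.

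**SAP 3.11.2.** Derive laboratory AE onset from the collection date. Class events from the baseline sample as prior even when it was collected on the day of first application. Check that the data-handling document says the same.

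**Cost.** A short protocol clarification and one derivation rule, with no extra sampling. Two small tasks come with it: same-day samples need a collection time or a before/after-application flag, and the team should confirm that the parent studies capture clinically significant Visit 13 results. The change does not bring Day 182 findings into the treatment-emergent tables for early courses; that follows from the 30-day window and is a separate matter.

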13. ADVERSE EVENTS

13.1. Definitions

13.1.1. Adverse Events (AEs)

An adverse event (AE) is any untoward medical occurrence in a patient that develops or worsens in severity during the conduct of a clinical study of a pharmaceutical product and does not necessarily have a causal relationship to the study drug. An adverse event can, therefore, be any unfavorable and unintended physical sign, symptom, or laboratory parameter that develops or worsens in severity during the course of the study, or significant worsening of the disease under study (or any concurrent disease), whether or not considered related to the study drug.

Accordingly, an adverse event could include any of the following:

- intercurrent illnesses;
- physical injuries;
- events possibly related to concomitant medication;
- significant worsening (change in nature, severity, or frequency) of the disease under study or other pre-existing conditions. (NOTE: A condition, recorded as pre-existing, that is intermittently symptomatic [e.g., headache] and which occurs during the study should be recorded as an adverse event);
- Drug interactions;
- Events occurring during diagnostic procedures or any washout phase of the study;
- laboratory or diagnostic test abnormalities occurring after the start of the study (i.e., after screening and once confirmed by repeat testing) that results in the withdrawal of the patient from the study, requires medical treatment or further diagnostic work-up, or is considered by the study investigator to be clinically significant. NOTE: Abnormal laboratory test results at the screening visit that preclude a patient from entering the study or receiving study treatment are not considered adverse events, but will be recorded to monitor data from patients who do not meet screening criteria.

The investigator must, for any common wart related AE, question the subject in detail to determine if there are any confounding factors (e.g., irritation by clothing or activity, sunburn) for any such AE.

The investigator should, when certain, report a diagnosis rather than the signs, symptoms or clinically relevant abnormal laboratory values associated with the AE. Otherwise, signs, symptoms or abnormal laboratory values may be used to describe the AE.

Any CS abnormality discovered prior to the first study medication treatment should be reported as medical history, not as an AE.

13.1.2. Serious Adverse Events (SAEs)

A Serious Adverse Event is any untoward medical occurrence that at any dose:

- Results in death;
- Is life threatening;
- Requires inpatient hospitalization or prolongation of existing hospitalization;
- Results in persistent or significant disability/incapacity,
- Is a congenital anomaly/birth defect or
- Is an important medical event.

The term “life threatening” refers to an event in which the subject was at risk of death at the time of event; it does not refer to an event that hypothetically might have caused death if it was more severe.

Inpatient hospitalization is considered to have occurred if the subject is admitted to the hospital on an in-patient basis, even if released the same day. Prolongation of hospitalization is defined as an additional night stay in the hospital. Hospitalization for elective treatment of a pre-existing condition that did not worsen from baseline is not considered an AE.

Important medical events are those that may not be immediately life threatening, result in death or hospitalization, but are clearly of major clinical significance and may jeopardize the subject or require intervention to prevent one of the outcomes listed in the SAE definition above. These should also usually be considered serious. Examples of such events are intensive treatment in an emergency room or at home for allergic bronchospasm, blood dyscrasia or convulsions that do not result in hospitalization.

